10.3.3 Other Analyses

Table 10.3.3-1: Pharmacokinetic Analyses for BMS-986242 and Nivolumab

Endpoint	Statistical Analysis Methods
BMS-986242	
C _{max} , AUC(TAU), AUC(0-T), AUC(INF), C _{trough} , CLT/F, V _{ss} /F, AI, %UR ₂₄ , %UR ₇₂ , MR_C _{max} , MR_AUC(TAU)	Summary statistics: geometric means and coefficients of variation
C _{max} , AUC(TAU), AUC(INF) (Only)	Scatter plots vs dose for each day measured; dose proportionality based on a power model and a CI around the power coefficient
T-HALF	Summary statistics: means and standard deviations
T _{max} .	Summary statistics: medians and ranges

Table 10.3.3-1: Pharmacokinetic Analyses for BMS-986242 and Nivolumab

Endpoint	Statistical Analysis Methods
Ctrough and Ceoi	Summary statistics to assess attainment of steady state: geometric means and coefficients of variation, by treatment and by day; plots vs time by dose
Nivolumab	
Ctrough and Ceoi	Summary statistics: geometric means and coefficients of variation, by treatment and by day, plots vs time by dose

Abbreviations: AI = accumulation index, calculated based on ratio of AUC and Cmax at steady state to after the first dose; AUC(0-T) = area under the concentration-time curve from time zero to the time of the last quantifiable concentration; AUC(TAU) = area under the concentration-time curve in one dosing interval; Ceoi = concentration at the end of infusion; CLT/F = apparent total body clearance; Cmax = maximum observed concentration; Ctrough = trough observed plasma concentration; Tmax = time of maximum observed concentration; Vss/F = apparent volume of distribution at steady-state.

Geometric means and geometric mean ratios for Cmax and AUC(0-T) will be estimated for participants in the substudy exploring food effect. PK time-concentration data may be pooled with data from other studies for PPK analysis, which will be presented in a separate report.

A concentration-response analysis may be used to characterize the effects of BMS-986242 on QTcF, based on data from the clinical pharmacology substudy QTc assessment. Additional ECG data and time matched concentrations may be pooled from other studies to perform an integrated analysis. The results of the analysis will be reported separately.

[REDACTED]	[REDACTED]

[REDACTED]

Table 10.3.3-3: Immunogenicity Analyses

Endpoint	Statistical Analysis Methods
Incidence of ADA to nivolumab in combination with BMS-986242	Frequency distribution of baseline ADA-positive participants and ADA-positive participants after initiation of the treatment
Baseline ADA-positive participant is defined as a participant who has a ADA detected sample at baseline. ^a ADA-positive participant is a participant with at least 1 ADA-positive sample relative to baseline after initiation of the treatment	

^a Baseline sample is the last sample before initiation of the treatment
Abbreviations: ADA = anti-drug antibody.

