Pharmacokinetic Assessments	See Section 9.5.3 and Table 9.5.3-1 .				On Day 1, a single dose of BMS-986242 will be administered under fasting condition; a 7-day washout period will follow during which serial PK samples with time-matched serial ECGs will be collected. For food effect participants only, on Day 8, selected dose level of BMS-986242 will be administered with a high-fat meal; a 2-day washout period will follow during which serial PK samples will be collected.
Study Treatment Administration	Details regarding preparation and administration are provided in the site training materials.				
BMS-986242 Administration	X		X ^a		

Abbreviations: AE = adverse event; ALT = alanine aminotransferase; AST = aspartate aminotransferase; BMS EDC = Bristol-Myers Squibb Electronic Data Capture; BUN = blood urea nitrogen; CBC = complete blood count; ECG = electrocardiogram; EOT = end of treatment; eSAE = electronic serious adverse event; GGT = gamma-glutamyl transferase; hCG = human chorionic gonadotropin; IP = investigational product; IRT = Interactive Response Technology; LDH = lactate dehydrogenase; LFT = liver function test; PE = physical examination; SAE = serious adverse event; WOCBP = women of childbearing potential.

^a Day 8 and 9 for food effect participants only

^b For Cycle 00 Day 1 and Day 8, PE and laboratory tests do not need to be repeated if completed within the last 72 hours (for all laboratory tests).

^c Participants who meet discontinuation criteria during or after Cycle 00 will have CBC with differential, platelets, and chemistry with LFTs done at the EOT and during the follow-up visit at 7 days.

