The dose-escalation planned dose levels for selection of the MTD/MAD/alternative dose is depicted in Table 5.1.2.1-1 and [Figure 5.1.2.1-1](#).

Table 5.1.2.1-1: Dose Escalation Schedule

Dose Level	BMS-986242	Nivolumab
1	12.5 mg	480 mg IV Q4W
2	25 mg	480 mg IV Q4W
3	50 mg	480 mg IV Q4W
4	100 mg	480 mg IV Q4W
5	200 mg	480 mg IV Q4W
6	400 mg	480 mg IV Q4W
7	600 mg	480 mg IV Q4W

Figure 5.1.2.1-1: Study Design Schematic - Dose Escalation

Clinical Pharmacology Substudy:

A clinical pharmacology substudy will be conducted to characterize the PK profile of BMS-986242 after a single-dose administration, BMS-986242 exposure-QTc relationship and to evaluate of the effect of food on the bioavailability of BMS-986242. The substudy will evaluate selected dose levels that have already been determined to be tolerable during dose escalation.

Participants in the substudy will receive a single dose of BMS-986242 under fasting condition on Cycle 00 (Day 1) followed by a 7-day washout period during which serial PK samples will be collected (Table 9.5.3-2). Triplicate ECGs will be collected at predose and select time points postdose on Day 1 (with matching PK samples) to allow the assessment of the effect of BMS-986242 exposure on QTc intervals. All participants will then receive BMS-986242 under the usual dosing condition with a light meal once daily in combination with nivolumab on Cycle 1 Day 1 and will follow all assessments as per Table 2-3. The inclusion criteria used in the dose-escalation phase apply to participants enrolled in the clinical pharmacology substudy (Section 6.1). The doses to be evaluated in the substudy will be determined based on available safety, PK and biomarker data. At least 3 doses (below, at, and above the expected dose for expansion) are expected to be evaluated in at least 6 evaluable participants per dose level in the substudy. Additional dose levels at may be evaluated if warranted.

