At a designated dose level, an exploratory food effect evaluation will be conducted. After receiving a single dose of BMS-986242 under fasting condition on Cycle 00 (Day 1) followed by a 7-day washout period, participants will receive 1 dose of BMS-986242 with a high-fat meal on Day 8. Serial PK samples will be collected during a 2-Day washout period (Table 9.5.3-2). Participants will then receive BMS-986242 under the usual dosing condition with a light meal once daily in combination with nivolumab on Cycle 1 Day 1 and will follow all assessments as per Table 2-3. For the dose to be evaluated in the food effect substudy, either a higher dose would need to be demonstrated to be safe in the dose-escalation phase or sufficient exposure multiples should have been obtained following multiple doses at the same dose level. Additional doses may be evaluated if warranted.

Study design schematics for the clinical pharmacology substudy are shown in Figure 5.1.2.1-2 (single-dose PK and exposure-QTc assessment) and Figure 5.1.2.1-3(food effect).

Figure 5.1.2.1-2: Study Design Schematic for the Clinical Pharmacology Substudy
Single-dose PK and Exposure-QTc Assessment (Selected Dose Levels)

[figure not shown]
[figure not shown]

Figure 5.1.2.1-3: Food Effect Assessment (Designated Dose Group*)
Food Effect Assessment (Designated Dose Group*)

* A designated dose group from the selected dose levels will be evaluated for both single-dose

PK/exposure-QTc and food effect. One cohort of at least 6 evaluable participants will be included.

Up to approximately 78 participants are planned to be enrolled for Part 1 (dose escalation) and clinical pharmacology substudy: approximately 30 participants for the dose-escalation phase, with up to 24 additional participants in Part 1 for additional characterization of the safety, PK, and pharmacodynamic profile of BMS-986242, and approximately 24 participants for the clinical pharmacology substudy (including food effect).

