9.5 Pharmacokinetic

9.5.1 Pharmacokinetic Assessment Following BMS-986242 Monotherapy

The PK of BMS-986242 and its metabolites (if applicable) will be derived from plasma concentration versus time and urinary excretion data. Individual participant PK parameter values will be derived by noncompartmental methods by a validated PK analysis program. Actual times will be used for the analyses.

The PK parameters to be assessed for BMS-986242 and selected metabolites following single-dose administration in Cycle 00 and multiple-dose administration in Cycle 0 include but are not limited to:

C _{max}	Maximum observed plasma concentration
T _{max}	Time of maximum observed plasma concentration
AUC(0-T)	Area under the concentration-time curve from 0 to last observed collection time (clinical pharmacology substudy)
AUC(INF)	Area under the concentration-time curve from 0 extrapolated to infinity time (clinical pharmacology substudy only)
AUC(TAU)	Area under the concentration-time curve in 1 dosing interval
C _{trough}	Trough observed plasma concentration at the end of the dosing interval
CLT/F	Apparent total body clearance
V _{ss} /F	Apparent volume of distribution at steady-state
T-HALF	Apparent terminal phase half-life
AI	Accumulation index, calculated based on ratio of AUC and C _{max} at steady state to after the first dose
%UR24	Percent urinary recovery over 24 hours
%UR72	Percent urinary recovery over 72 hours (clinical pharmacology substudy only)

In addition, the following PK parameters for select BMS-986242 metabolites may also be assessed if data permit:

MR_C _{max}	Ratio of metabolite C _{max} to parent C _{max} , corrected for molecular weight
MR_AUC(TAU)	Ratio of metabolite AUC(TAU) to parent AUC(TAU), corrected for molecular weight
MR_AUC(0-T)	Ratio of metabolite AUC(0-T) to parent AUC(0-T), corrected for molecular weight (clinical pharmacology substudy only)
MR_AUC(INF)	Ratio of metabolite AUC(INF) to parent AUC(INF), corrected for molecular weight (clinical pharmacology substudy only)

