Table 9.5.3-1: Pharmacokinetic, Anti-drug Antibody (ADA/Immunogenicity) Sampling Schedule for BMS-986242 and Nivolumab (Dose Escalation Part 1 and Dose-Expansion Cohorts Part 2)

Study Day of Sample Collection	Event	Time (Relative To BMS-986242 Dosing) Hour:Min	BMS-986242 and Metabolites Plasma Sample	BMS-986242 Plasma Sample (Biotransformation)	BMS-986242 and Metabolites Urine Sample	Nivolumab Serum Sample	Nivolumab ADA Sample
	EOI ^b	01:00	X			X	
		02:00	X				
		04:00	X				
C3D1	Predose	00:00	X			X	X
	EOI	01:00	X			X	
Every 4 Cycles from C5D1	Predose	00:00	X			X	X
EOT			X			X	X
FUC ^c			X			X	X

Note: Each treatment cycle is 4 weeks (except Cycle 0).

Abbreviations: ADA = anti-drug antibody; EOI = end of infusion; FU = follow-up.

^a This sample should be taken 24 hours after the previous BMS-986242 dose on Cycle 0 Day 14 if Cycle 1 Day 1 does not occur on the next day after Cycle 0 Day 14.

^b This sample should be taken preferably within 2 minutes prior to the end of infusion. If the end of infusion is delayed to beyond the nominal infusion duration, the collection of this sample should also be delayed accordingly.

^c Performed at the first 2 follow-up visits (up to 100 days from the EOT visit) EXCEPT for participants who have WITHDRAWN CONSENT.

Table 9.5.3-2: Pharmacokinetic Sampling and ECG Collection Schedule for BMS-986242 in the Clinical Pharmacology Substudy

Study Day of Sample Collection	Event	Time (Relative to BMS-986242 Dose) Hour: Min	BMS-986242 and Metabolites Plasma Sample	BMS-986242 and Metabolites Urine Sample	ECG
C00D1	Predose	-01:00			X
C00D1	Predose	-00:45			X
C00D1	Predose	-00:30			X
C00D1	Predose	00:00			
		01:00	X	X (0-8 h)	
		01:45			X
		02:00	X		
		02:45			X
		03:00	X		
		03:45			X
		04:00	X		
		06:00	X		
		08:00	X		
C00D2		24:00	X		X (8-24 h)
C00D3		48:00	X	X (24-48 h)	
C00D4		72:00	X	X (48-72 h)	

Table 9.5.3-2: Pharmacokinetic Sampling and ECG Collection Schedule for BMS-986242 in the Clinical Pharmacology Substudy

Study Day of Sample Collection	Event	Time (Relative to BMS-986242 Dose) Hour: Min	BMS-986242 and Metabolites Plasma Sample	BMS-986242 and Metabolites Urine Sample	ECG
C00D8 ^{a,b}	Predose	00:00 ^b	X	X	
		01:00	X	X (0-8 h)	
		02:00	X		
		03:00	X		
		04:00	X		
		06:00	X		
		08:00	X		
C00D9 ^a		24:00	X	X (8-24 h)	
C00D10 ^a		48:00 ^c	X		

Abbreviations: ADA = anti-drug antibody; EOT = end of treatment; FU = follow-up.

^a Exploratory food effect cohort only.

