^b For participants not in the Food Effect cohort, C00D8 predose samples should be taken approximately 168 hours after dosing on Cycle 00 Day 1 if Cycle 1 Day 1 does not occur on the next day after Cycle 00 Day 7.

^c For participants in the Food Effect cohort, this sample should be taken 48 hours after dosing on Cycle 00 Day 8 if Cycle 1 Day 1 does not occur on the next day of Cycle 00 Day 9.

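### The food-effect AUC(0-T) ratio compares a 72 h fasted profile with a 48 h fed profile, so it is biased low if drug is still quantifiable at 72 h

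*Combined protocol and SAP*

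**What the plan says.** For the food effect, Section 10.3.3 plans: "Geometric means and geometric mean ratios for Cmax and AUC(0-T) will be estimated for participants in the substudy exploring food effect". AUC(INF) is a listed substudy parameter and will be summarised, but it is not named for this ratio. The direction of the ratio (fed/fasted or the reverse) is not stated.

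AUC(0-T) has two definitions:

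- Section 9.5.1: "Area under the concentration-time curve from 0 to last observed collection time (clinical pharmacology substudy".
- Abbreviations to Table 10.3.3-1: "area under the concentration-time curve from time zero to the time of the last quantifiable concentration".

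The two periods are sampled for different lengths of time:

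- **Fasted (Cycle 00 Day 1).** Section 5.1.2.1 describes a dose "followed by a 7-day washout period during which serial PK samples will be collected". Table 9.5.3-2 lists plasma at 1, 2, 3, 4, 6, 8, 24, 48 and 72 h.
- **Fed (Cycle 00 Day 8).** Section 5.1.2.1 states: "Serial PK samples will be collected during a 2-Day washout period". Table 2-5 agrees: "a 2-day washout period will follow during which serial PK samples will be collected". Table 9.5.3-2 lists plasma at 1, 2, 3, 4, 6, 8, 24 and 48 h. Footnote c says of the last of these that "this sample should be taken 48 hours after dosing on Cycle 00 Day 8" if Cycle 1 Day 1 is not the day after Day 9.

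**The concern.** A food-effect ratio should differ from 1 only because food changed exposure. Here the fasted area can include a 48-72 h segment that the fed area can never include. If T is the last collection time, the windows differ by schedule. If T is the last quantifiable concentration, they differ whenever the fasted 72 h sample is quantifiable.

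The error has one direction: it lowers fed relative to fasted exposure. A small true increase with food could read as no effect, and no effect could read as a small decrease. Cmax is untouched, but it measures peak. AUC(0-T) is the only extent-of-exposure measure that the visible text names for the ratio.

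**Working it through.** **1. The plan's own figure.** Section 10.1.1 gives precision for n = 6 with log-scale SDs of 0.23 (Cmax) and 0.22 (AUC(0-T)). The 90% CI half-width on the log scale, with 80% assurance, is

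t(0.95, 5 df) × SD × √(χ²(0.80, 5 df)/5) / √6.

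- Cmax: 0.2285, giving 79.6% to 125.7%.
- AUC(0-T): 0.2185, giving 80.4% to 124.4%.

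Both match the plan. These limits describe each geometric mean, not the fed/fasted ratio, and the window problem does not change them.

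**2. Inputs for the window effect.**

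- Last serial plasma sample: 72 h fasted, 48 h fed (Table 9.5.3-2).
- Half-life: 13 h, predicted (Section 7.4.1). Every other half-life below is an assumption.
- True food effect: none, so an unbiased ratio equals 1.

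**3. Expected fed/fasted ratio.** For mono-exponential decline with half-life h, the expected ratio is

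AUC(0-48)/AUC(0-72) = (1 − 2^(−48/h)) / (1 − 2^(−72/h)).

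| Half-life | Share of AUC(INF) after 48 h | Share after 72 h | Ratio |
|---|---|---|---|
| 8 h (assumed) | 1.6% | 0.2% | 0.986 |
| 13 h (protocol) | 7.7% | 2.2% | 0.943 |
| 20 h (assumed) | 18.9% | 8.2% | 0.883 |
| 26 h (assumed) | 27.8% | 14.7% | 0.846 |

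At 13 h the arithmetic is 0.9226/0.9785 = 0.943. Since 1/0.943 = 1.06, a true 6% increase with food would read as 1.00.

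**4. Check with absorption and the scheduled times.** This uses a one-compartment oral model at 13 h, the sampling times above, and a linear-up/log-down trapezoid. The absorption rates are assumed.

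| ka (per h) | Ratio | 72 h level as % of Cmax |
|---|---|---|
| 0.5 | 0.935 | 3.2% |
| 1 | 0.939 | 2.7% |
| 2 | 0.941 | 2.4% |

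The simple formula therefore does not overstate the effect.

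**5. When the bias occurs.** Under the last-quantifiable definition, the assay limit would have to lie below about 2.4% to 3.2% of Cmax in this model. The documents give no assay limit, so this cannot be settled. If nothing is quantifiable after 48 h, both areas stop by 48 h and this bias vanishes.

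**6. The Day 8 predose sample.** It falls about 168 h after the fasted dose. Read literally, the last-collection-time definition could extend the fasted area to 168 h, giving 0.9226/0.9999 = 0.923 at 13 h. Only about 0.01% of drug remains by then, so carry-over into the fed period is negligible.

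**7. With a common window.** Restricting both periods to 0-48 h gives an expected ratio of 1.000 under no food effect at every half-life tried.

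**The case against.** The strongest reply is that this is small and easily settled later. Section 10.3 calls itself a summary and defers to a statistical analysis plan finalised before database lock. The parameter list in Section 9.5.1 is open-ended, so a 0-48 h area could be derived without an amendment. AUC(INF) will be summarised anyway, and at 13 h little of it is extrapolated, so a reader could notice the truncation. A 6% shift is small beside limits of roughly 20% to 25% around each geometric mean. No stated decision rule uses the ratio. The half-life is a prediction for a drug with no prior human data, and the bias may not arise at all if the 72 h samples are below the assay limit.

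Much of this stands as a limit on importance. It does not remove the defect. Section 10.3.3 does not leave the parameter open: it names AUC(0-T) for the ratio and defines it. A separate AUC(INF) summary does not correct that ratio. The precision limits concern random error in each mean, whereas the window error is systematic and would not shrink with more participants. Uncertainty about half-life works both ways, since a longer one enlarges the bias. The two definitions of AUC(0-T) need reconciling in any case.

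**Conclusion.** The point holds, conditionally. As written, the plan gives a downward-biased fed/fasted AUC(0-T) ratio under the last-collection-time definition, and under the last-quantifiable definition whenever the fasted 72 h sample is quantifiable. The size is about 6% at the protocol's 13 h half-life (6% to 7% with absorption modelled), about 1% at 8 h and about 15% at 26 h. These figures assume no true food effect, first-order elimination with the same half-life in both periods, and a fed/fasted direction. The schedule mismatch and the lack of a common window are certain from the text; whether the bias will be material is not. Given the exploratory aim, one cohort of at least 6 evaluable participants and no equivalence criterion, this should be corrected but does not threaten the trial's main conclusions.

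**What to change.** In Section 10.3.3:

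- Compute the food-effect AUC ratio over 0-48 h in both periods, and state that it is fed/fasted.
- Say that the Cycle 1 Day 1 predose sample supplies the fed 48 h value when Cycle 1 starts on Day 10.
- Report the AUC(INF) ratio as support where it can be estimated, with the extrapolated fraction for each period.

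Use a single definition of AUC(0-T) in Sections 9.5.1 and 10.3.3.

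The cost is analysis wording only. A 48 h concentration is already scheduled in each period, so no samples or participants are added. The 48-72 h fasted data drop out of the main food-effect ratio but still serve AUC(INF), half-life and the single-dose PK summary.

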10.3.4 Interim Analyses

Administrative interim analysis for internal decision making or external publication purposes may be performed. No formal inferences requiring any adjustment to statistical significance level will be performed.

12 APPENDICES

APPENDIX 1 ABBREVIATIONS AND TRADEMARKS

Term	Definition
ADA	anti-drug antibody
ADME	absorption, distribution, metabolism, and excretion
AE	adverse event
AI	accumulation index
ALT	alanine aminotransferase
APC	antigen-presenting cell
AST	aspartate aminotransferase
AUC	area under the concentration-time curve
AUC(0-24)	area under the concentration-time curve from time zero to 24 hours postdose
AUC(INF)	area under the concentration-time curve from time zero to infinity
AUC(TAU)	area under the concentration-time curve in 1 dosing interval
BCRP	breast cancer resistance protein
BLRM	Bayesian Logistic Regression Method
BMS	Bristol-Myers Squibb
BOR	best overall response
BUN	blood urea nitrogen
C24	observed plasma concentration at 24 hours
CBC	complete blood count
C _{ei}	concentration at the end of infusion
CI	confidence interval
CLT/F (or CLT)	apparent total body clearance
C _{max}	maximum observed plasma concentration
C _{maxss}	steady-state peak concentration
CNS	central nervous system
CR	complete response
CrCl	creatinine clearance
CRF	case report form
CT	computed tomography

Term	Definition
CTLA-4	cytotoxic T lymphocyte-associated antigen 4
Ctrough	trough observed plasma concentration at the end of the dosing interval
CYP	cytochrome P450
DDI	drug-drug interaction
DILI	drug-induced liver injury
DLT	dose-limiting toxicity
DNA	deoxyribonucleic acid
DOR	duration of response
ECG	electrocardiogram
ECOG	Eastern Cooperative Oncology Group
ELISA	enzyme-linked immunosorbent assay
EOI	end of infusion
EOT	end of treatment
FDG	fludeoxyglucose
FNR	false negative rate
FPR	false positive rate
FU	follow-up
GGT	gamma-glutamyl transferase
HDPE	high-density polyethylene
HNSTD	highest non-severely toxic dose
HPV	human papillomavirus
IB	Investigator Brochure
IC50	half-maximal inhibitory concentration
ICF	informed consent form
IDO1	indoleamine 2,3-dioxygenase 1
IFN γ	interferon-gamma
IHC	immunohistochemistry
IMP	investigational medicinal products
I-O	immuno-oncology
IP	investigational product

Term	Definition
IV	intravenous
IRT	interactive response technology
LC-MS	liquid chromatography-mass spectrometry
LFT	liver function test
mDOR	median duration of response
MedDRA	Medical Dictionary for Regulatory Activities
miRNA	micro ribonucleic acid
MR_AUC(TAU)	ratio of metabolite AUC(TAU) to parent AUC(TAU), corrected for molecular weight
MR_Cmax	ratio of metabolite Cmax to parent Cmax, corrected for molecular weight
MRI	magnetic resonance imaging
MRS	maximum recommended starting dose
MTD	maximum tolerated dose
NA	not applicable
NCI CTCAE	National Cancer Institute Common Terminology Criteria for Adverse Events
NHL	non-Hodgkin's lymphoma
NOAEL	no-observed adverse effect level
NSCLC	non-small cell lung cancer
ORR	objective response rate
OS	overall survival
OSR	overall survival rate
PBMC	peripheral blood mononuclear cells
PCR	polymerase chain reaction
PD	progressive disease
PD-1	programmed cell death-1
PD-L1	programmed death receptor-ligand 1
PE	physical examination
PET	positron emission tomography
PFSR	progression-free survival rate
P-gp	P-glycoprotein

Term	Definition
PI	principal investigator
PK	pharmacokinetic(s)
PPK	population pharmacokinetics
PO	per os, orally
PR	partial response
PT	preferred term
Q2W	every 2 weeks
Q4W	every 4 weeks
QD	quaque die, once daily
QTcF	QT interval corrected for heart rate using Fridericia's formula
RCC	renal cell carcinoma
RECIST	Response Evaluation Criteria in Solid Tumors
SAE	serious adverse event
SD	stable disease
SCCHN	squamous cell carcinoma of the head and neck
SD	stable disease
SNP	single nucleotide polymorphism
STD10	severely toxic dose to 10%
TCGA	The Cancer Genome Atlas
TDO	tryptophan 2,3-dioxygenase
Teff	effector T cells
T-HALF	apparent elimination half-life
Tmax	time of maximum observed plasma concentration
tMLR	tolerogenic mixed lymphocyte reaction
Treg	regulatory T cells
TSH	thyroid-stimulating hormone
UGT1A1	uridine diphosphate glucuronosyltransferase 1A1
ULN	upper limit of normal
%UR24	percent urinary recovery over 24 hours
%UR72	percent urinary recovery over 72 hours

Term	Definition
US	United States
VS	vital signs
V _{ss} /F (or V _{ss})	apparent volume of distribution at steady state
WBC	white blood cell
WOCBP	women of childbearing potential

